5.2 Objectives

The objective of this clinical investigation is to evaluate the therapeutic efficacy of microdosing BurstDR[™] stimulation in spinal cord stimulation (SCS) patients with chronic intractable back and/or leg pain.

5.2.1 Primary Objectives

• To evaluate efficacy of microdosing BurstDR[™] stimulation in patients with chronic intractable back and/or leg pain that have never received neuromodulation treatments before.

5.2.2 Secondary Objectives

- Evaluate the optimal microdosing program required to maintain optimal pain relief on a patient specific basis
- Evaluate the long term efficacy of BurstDR[™] stimulation on patients' pain intensity
- Evaluate the improvements in quality of life, disability, anxiety, depression, catastrophizing, medication and overall satisfaction of patients using microdosing BurstDR[™] stimulation

5.3 Endpoints

There is 1 primary endpoints and 7 secondary endpoints in this clinical investigation.

5.3.1 Primary Endpoint

• Evaluate the change in pain intensity between baseline, trial and long-term follow up evaluations using the Visual Analog Scale (VAS) assessments.

5.3.2 Secondary Endpoint

- Evaluate the optimal microdosing program required to maintain optimal pain relief on a patient specific basis
- Evaluate the change in European Quality of life 5 Dimensions (EQ-5D) scores between baseline, SCS trial and follow up visits
- Evaluate the change in Oswestry Disability Index (ODI) scores between baseline, SCS trial and follow up visits
- Evaluate the change in Hospital Anxiety and Depression Scale (HADS) scores between baseline, SCS trial and follow up visits
- Evaluate the change in Pain Catastrophizing Scale (PCS) scores between baseline, SCS trial and follow up visits
- Evaluate the change in Patient Global Impression of Change (PGIC) between SCS trial and follow up visits
- Evaluate the change in medication usage between baseline, SCS trial and follow up visits

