1.8 Study Assessments

Subjects will undergo a baseline assessment to collect primary and secondary outcome measures prior to the SCS trial. Specifically, baseline assessments will include: pain rating as assessed by the VAS, quality of life as assessed by EQ-5D, disability as assessed by ODI, anxiety and depression as assessed by the HADS, and pain catastrophizing as assessed by the PCS. Medication usage will also be collected during the baseline visit.

Subjects will be implanted with trial SCS system according to clinical practice and practitioner's discretion. At the end of the SCS trial period, subjects who experienced a reduction of 50% or more in average pain back and/or leg VAS scores with one of the two microdosing stimulation paradigms will be offered permanent implant and further participation in the study. The same primary and secondary outcomes measures will be collected at the end of the SCS trial period as well as at the 1, 3 and 6 months follow up visit, with the inclusion of patient satisfaction as assessed by the PGIC. Programming parameters will also be assessed during these visits.

2 Introduction

This document is a clinical investigation plan (CIP) for the BOLD clinical investigation. This clinical investigation is intended to evaluate the therapeutic efficacy of microdosing BurstDR[™] stimulation in

spinal cord stimulation (SCS) patients with chronic intractable back and/or leg pain. This clinical investigation is sponsored by Abbott.

This clinical investigation will be conducted in accordance with this CIP. All parties involved in the conduct of the clinical investigation will be qualified by education, training, or experience to perform their tasks and this training will be documented appropriately.

3 Background and Justification for Clinical Investigation

Spinal cord stimulation (SCS) is increasingly being used as an alternative for the treatment of chronic, intractable pain. In a systematic meta-analysis of the literature, Taylor et al. (2006) reported that SCS reduces pain, improves quality of life, reduces analgesic use, allows some patients to return to work and may also result in significant cost savings over time, while having minimally significant adverse events in patients with neuropathic back and/or leg pain.

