5.1 Clinical Investigation Design

This is a prospective, open label, multicenter feasibility trial to evaluate the therapeutic efficacy of different BurstDR[™] microdosing patterns in patients with chronic intractable pain.

[figure not shown]
Subjects diagnosed with chronic intractable back and/or leg pain, with no prior history of SCS therapy, will be considered for inclusion in this study. After baseline evaluation, subjects will undergo a SCS trial using the Abbott Invisible Trial system. During the trial implant phase, SCS leads will be implanted in the dorsal column based on physician discretion. According to standard clinical practices performed in the United States (US), the trial phase will last around 3-7 days. At the start of the trial phase, patients will be

programmed with the first ON/OFF stimulation pattern (30 second STIM ON, 90 seconds STIM OFF). Patients who do not achieve adequate pain relief (at least 50% reduction in back and/or leg VAS from baseline) within the first 3-4 days will be reprogrammed to a new ON/OFF stimulation pattern (5 seconds ON/ 15 seconds OFF). Patients, who still do not achieve adequate pain relief within 2 to 3 days from reprogramming, will be reprogrammed to a continuous mode of BurstDR[™] stimulation and their trial evaluation will continue. These patients will be evaluated for an additional 2 days. At the end of the SCS trial, all subjects that experience at least 50% pain relief (according to average back and/or leg VAS) using one of the two microdosing burst stimulation paradigms will be considered further participation in the study. See Figure 1.

Patients who have passed the trial phase and have received permanent implantation will be programmed based on the stimulation mode used for their trial success. Pain intensity, quality of life, disability, anxiety, depression, pain catastrophizing, satisfaction, and medication usage will be assessed at baseline, after SCS trial and at the 1, 3 and 6 month follow up. Adverse events will be collected throughout the study period.

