6.4.3 End of Trial

During the End of Trial visit, subjects will complete the same questionnaires completed during the baseline visit. If the VAS score is < 50% of the VAS collected during the screening visit and is not using the two microdosing burst stimulation paradigms, the subject will exit the study. Subjects whose VAS score at the end of the trial is >50% of the VAS collected during the screening visit and is using one of the two microdosing burst stimulation paradigms, will be considered for permanent lead and IPG implantation.

The following assessments and information will be collected at the End of Trial visit:

- Clinical investigation specific examinations
 - Pain level as assessed by the VAS
 - Quality of life as assessed by the EQ-5D
 - Disability as assessed by the ODI
 - Anxiety and Depression as assessed by the HADS
 - Pain Catastrophizing as assessed by the PCS
 - Satisfaction as assessed by the PGIC
 - Medication usage;
 - Programming Form

Timing of visit	Activities at visit	Case Report Form
End of Trial	 Subject assess pain levels, quality of life, disability, anxiety, depression, pain catastrophizing, satisfaction, medication usage, and programming 	 VAS Form EQ-5D Form ODI Form HADS Form PCS Form PGIC Form Medication Usage Form Programming Form

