6.7 Study Flow Chart

The Study Flow Chart and the Table 2 below summarize subject flow and requirements of this clinical investigation.

Figure 1: Study Flow Chart

Visit	Enrollment	Baseline	SCS Trial	End of Trial	SCS Implant	Activation	Follow-up Visits*
Study Activity							
Informed Consent Process	х						
Inclusion/Exclusion Criteria Screening	х						
VAS Assessment		X		Х			Х
Enrollment Form	Х						
EQ-5D Assessment		X		X			Х
ODI Assessment		X		Х			Х
HADS Assessment		X		X			Х
PCS Assessment		X		X			Х
PGIC Assessment				X			Х
Trial System Implant			х				
Permanent System Implant					x	x	
Adverse Event	(X)	(X)	(X)	(X)	(X)	(X)	(X)
Deviation	(X)	(X)	(X)	(X)	(X)	(X)	(X)
Termination	(X)	(X)	(X)	(X)	(X)	(X)	(X)
Death	(X)	(X)	(X)	(X)	(X)	(X)	(X)

Table 2: List of all clinical investigation specific tests and procedures

(X) If applicable

* Follow up visit assessments will be performed at months $1(30 \pm 21 \text{ days})$, $3(90 \pm 21 \text{ days})$ and $(180 \pm 21 \text{ days})$

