7.1.1 Primary [Safety/Effectiveness] Endpoint Hypothesis(es)

7.1.1.1 Analysis Methodology

The primary analysis to assess improvement in pain intensity, using VAS, will be conducted using repeated measures ANOVA (RMANOVA). Post-hoc Tukey's pairwise comparisons will follow to determine specific differences between follow-up visits. Secondary analyses to assess improvements in quality of life, disability, anxiety, depression catastrophizing and satisfaction will be conducted using repeated measures ANOVA (RMANOVA) or the most appropriate statistical methods.

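### The PGIC endpoint is the change in a rating of change from End of Trial, so it shows movement after the trial phase and not improvement in satisfaction from before SCS

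*Combined protocol and SAP*

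**What the plan says.** Section 5.3.2 lists as a secondary endpoint "Evaluate the change in Patient Global Impression of Change (PGIC) between SCS trial and follow up visits"; section 1.4.2 has the same wording. The other questionnaire endpoints in that list include a baseline term, for example "Evaluate the change in Oswestry Disability Index (ODI) scores between baseline, SCS trial and follow up visits".

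PGIC is the satisfaction measure and comes in after baseline. Section 1.8 describes the End of Trial and follow-up assessments as the baseline set "with the inclusion of patient satisfaction as assessed by the PGIC". Section 6.4.1 (Baseline) does not list it. Section 6.4.3 (End of Trial) does: "Satisfaction as assessed by the PGIC". Section 6.4.6 repeats it for the follow-up visits. In the section 6.7 flow chart the row "PGIC Assessment" is marked at End of Trial and follow-up only.

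The design text disagrees. Section 5.1 says "Pain intensity, quality of life, disability, anxiety, depression, pain catastrophizing, satisfaction, and medication usage will be assessed at baseline", and sections 1.3 and 6 say the same.

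The secondary objectives in 5.2.2 include improvement in overall satisfaction. Section 7.1.1.1 says the secondary analyses assess improvements, and gives the method as "depression catastrophizing and satisfaction will be conducted using repeated measures ANOVA (RMANOVA"), followed at once by an allowance for another method if judged more suitable. The protocol does not give the PGIC response scale, its reference time point or a responder definition.

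**The concern.** Scales such as ODI measure a state, so a difference between visits is the change of interest. PGIC asks the subject to report the change directly. Subtracting the End of Trial rating from a follow-up rating removes the quantity the objective asks about and leaves only what happened after the trial phase.

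The End of Trial rating is also the earliest one available, so no contrast among the collected PGIC visits can reach back to the state before SCS. Only the level of the rating can do that, and the endpoint as worded is not the level.

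At stake is the reading of the satisfaction result. A cohort that improved and stayed improved could be reported as showing no change, and one that slipped slightly while still much better than before SCS could be reported as worse. Section 7.1 says the results may feed a later study with formal hypothesis testing, so a misread result could carry forward.

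**Working it through.** The plan gives no effect size, power or sample size figure for PGIC, so there is nothing to reproduce. The check is algebra, followed by an illustration.

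**Algebra.** Let m be the score for no change, P(0) the End of Trial rating, P(v) the rating at follow-up visit v, and D(v) = P(v) - P(0) the endpoint as worded.

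1. *Ratings against the state before SCS.* If a subject has benefit b at End of Trial and keeps it, P(0) = P(v) = m + b, so D(v) = 0 for every b. With no benefit, b = 0 and D(v) = 0 again. The contrast carries no information about b.
2. *Ratings against the previous visit.* With benefit b at End of Trial and stability afterwards, P(0) = m + b and P(v) = m, so D(v) = -b. A subject with no benefit throughout still has D(v) = 0. Sustained benefit would then score lower than no benefit.

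Neither result depends on the scale, the variance or the sample size.

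**Illustration under the first reading.** Inputs from the documents: four PGIC visits (End of Trial, months 1, 3 and 6; sections 6.4.3 and 6.4.6), type-1 error 0.05 (section 7.3) and at most 60 enrolled (section 7.4). Assumed, because the documents do not give them: a 1 to 7 scale with 4 = no change and higher = better; SD 1; between-visit correlation 0.5; complete data; n = 30, 40 or 60 at follow-up. Scores were rounded and limited to 1 to 7, with 4,000 runs per scenario. The test is the one-way repeated measures ANOVA F test for visit.

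| Scenario (means at the four visits) | Mean month 6 minus End of Trial | Rejection, n = 30 / 40 / 60 |
|---|---|---|
| Sustained improvement (6, 6, 6, 6) | 0.00 | 5.2% / 5.0% / 5.1% |
| No improvement (4, 4, 4, 4) | 0.00 | 5.0% / 5.5% / 5.1% |
| Small slip, still improved (6, 5.5, 5.5, 5.5) | -0.45 | 67% / 82% / 96% |
| Further gain (5, 5.5, 5.5, 5.5) | +0.48 | 71% / 84% / 97% |

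The first two rows cannot be told apart. In the third row the nominal month 6 mean is 5.5 - 4 = 1.5 points better than no change, yet the significant finding is a decline. The slip and gain are below the nominal 0.5 in size because of the rounding and limits.

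**The same data analysed as a level.** A one-sample t test of the month 6 rating against 4 rejects in 100% of runs when improvement is sustained. It rejects in 5.3%, 4.4% and 5.0% of runs (n = 30, 40, 60) when there is none. The level separates the cases that the contrast cannot.

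**The case against.** The strongest reply has four parts.

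*The method is open.* Section 7.1.1.1 permits a method other than repeated measures ANOVA, and section 7 says further analysis detail may be held in a separate SAP. Nothing forbids reporting visit means, from which a reader could see the level. This stands as far as it goes, but it frees the test and not the endpoint: any method applied to the difference as defined has the same limit.

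*The comparison has a use.* If ratings are against the state before SCS, comparing End of Trial with months 1, 3 and 6 asks whether the trial-phase impression lasts, which fits the long-term interest in section 5.2.2. This stands, and is why the comparison need not be deleted.

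*The reference point may be on the form.* Appendix D keeps the case report forms under separate cover. The form may define scale and reference. That would settle which reading applies, but it would not change the endpoint wording.

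*Little depends on it.* Section 7.1 requires no formal hypothesis test and section 7.6 sets no success criteria. This stands and limits the impact, although PGIC is not among the summary-only endpoints in 5.3.3.

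Two stronger readings are tempting and unsupported. A reader might infer that the planned analysis cannot show improvement of any kind. In the illustration it detects further gain after the trial in 71% to 97% of runs; what it cannot show is improvement from before SCS. A reader might also infer that sustained benefit always scores zero. That needs a fixed reference before SCS, which the protocol does not state.

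The 50% pain relief rule for continuing means the End of Trial rating is taken when subjects have been selected as responders. That rule uses VAS and affects the End of Trial reference for every follow-up measure, so it is context here and not a defect specific to PGIC.

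**Conclusion.** The concern holds in this form: the endpoint as worded does not measure what sections 5.2.2 and 7.1.1.1 say it is for. Under a reference before SCS it measures movement after the trial phase, with zero for both sustained and absent benefit and a negative value for a small slip in subjects still improved. Under a previous-visit reference it is not interpretable as improvement. This rests on the endpoint wording, the visit schedule and PGIC being a rating of change. The percentages and the values -0.45 and +0.48 rest on the assumed scale, SD, correlation and sample sizes and are illustrative only.

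The unchanged-at-4 scenario is a limiting case, since subjects who continue have met the pain relief rule. It shows what the contrast leaves out and is not a prediction.

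Separately, the design text in 1.3, 5.1 and 6 contradicts 1.8, 6.4.1, 6.4.3 and the flow chart on whether satisfaction is assessed at baseline. The detailed visit sections agree with one another, so this looks like a drafting slip in a collective list. It matters because it may suggest a baseline PGIC value that the schedule does not provide.

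Overall impact is limited, for the reasons given under the objection. The correction is still worth making because it costs almost nothing and lets the endpoint answer its stated objective.

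**What to change.** 1. In 1.4.2 and 5.3.2, define the endpoint as the PGIC rating itself at End of Trial and at months 1, 3 and 6, each made against the state before the SCS trial. State the response scale and its direction.
2. Summarise it at each visit as the distribution over categories and the proportion much or very much improved, with confidence intervals. Match the category names to the form, and show the number of subjects rated and missing, since 7.1.1.3 rules out imputation.
3. In 7.1.1.1, take satisfaction out of the repeated measures ANOVA list. Keep any comparison of End of Trial with follow-up as a supportive durability analysis, with a named method suited to ordinal data, such as a signed-rank test or an ordinal mixed model.
4. Reconcile 1.3, 5.1 and 6 with 1.8, 6.4.1, 6.4.3 and 6.7 on baseline satisfaction. Section 6.5 also omits PGIC from its list of patient-reported measures and could be aligned in the same edit.

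Cost: the wording of one endpoint in two places, one analysis sentence and the collective lists, plus a check that the PGIC form's instruction gives the intended reference point. If it does not, that instruction changes too. No new visits or measurements are needed, and the durability comparison is retained.

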5.3.3 Descriptive Endpoint(s)

Descriptive endpoints are reported using only summary statistics and no hypothesis tests will be performed.

- Optimal microdosing program
- Medication Usage

5.4 Study Population

The intended population of this clinical investigation consists of patients diagnosed with chronic intractable back and/or leg pain with no prior history of neuromodulation therapies.

5.4.1 Inclusion Criteria

- Subject is able to provide informed consent to participate in the study;
- Subject diagnosed with chronic intractable pain associated with back and/or limbs;
- Subject is 18 years of age or older;
- Subject has failed to respond to at least 6 months of conventional treatment which may include pharmacological treatment, physical therapy, epidural injections;
- Subject has a back and/or leg pain intensity of at least 6.0 cm out of 10.0 cm on the average back and/or leg pain VAS at baseline;
- Subject's medical record has been evaluated by the Investigator to ensure that the subject is a
 good candidate for a neurostimulation system;
- Subject is on stable pain medications with a total opioid for at least 28 days prior to enrolling in this study, and is willing to stay on those medications with no dose increase until the 3 month visit;
- Subject is willing to cooperate with the study requirements including compliance with the regimen and completion of all office visits;
- Female candidates of child-bearing potential agree to commit to the use of an effective method of contraception (including but not limited to sterilization, barrier devices, oral contraceptives, intrauterine devices (IUDs), condoms, rhythm method, or abstinence) for the duration of the study

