- Quality of life as assessed by the European Quality of Life 5 Dimensions (EQ-5D)
- Disability as assessed by the Oswestry Disability Index (ODI)
- Anxiety and Depression as assessed by the Hospital Anxiety and Depression Scale (HADS)
- Pain Catastrophizing as assessed by the Pain Catastrophizing Scale (PCS)
- Satisfaction as assessed by the Patient Global Impression of Change (PGIC)
- Medication Usage
- Adverse Events

After baseline evaluation, subjects will undergo a SCS trial using the Abbott Invisible Trial system. During the trial implant phase, SCS leads will be implanted in the dorsal column based on physician discretion. According to standard clinical practices performed in the United States (US), the trial phase will last around 3-7 days. At the start of the trial phase, patients will be programmed with the first ON/OFF stimulation pattern (30 second STIM ON, 90 seconds STIM OFF). Patients who do not achieve adequate pain relief (at least 50% reduction in back and/or leg VAS from baseline) within the first 3-4 days will be reprogrammed to a new ON/OFF stimulation pattern (5 seconds ON/ 15 seconds OFF). Patients, who still do not achieve adequate pain relief within 2 to 3 days from reprogramming, will be reprogrammed to a continuous mode of BurstDR[™] stimulation and their trial evaluation will continue. These patients will be evaluated for an additional 2 days. At the end of the SCS trial, all subjects that experience at least 50% pain relief (according to average back and/or leg VAS) using one of the two microdosing burst stimulation paradigms will be considered further participation in the study. See Figure 1.

Patients who have passed the trial phase and have received permanent implantation will be programmed based on the stimulation mode used for their trial success. Pain intensity, quality of life, disability, anxiety, depression, pain catastrophizing, satisfaction, and medication usage will be assessed at baseline, after SCS trial and at the 1, 3 and 6 month follow up. Adverse events will be collected throughout the study period.

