6.4.1 Baseline

Baseline visit activities can occur at the same visit of enrollment after the informed consent has been obtained.

The following assessments and information will be collected at the baseline visit

- Demographics- include subject's Age and Gender
- Physical examination- include subject's height and weight
- Indication for device/ procedure
- Previous therapies tried for indications
- Clinical investigation specific examinations
 - Pain intensity as assessed by the VAS
 - Quality of life as assessed by the EQ5D
 - Disability as assessed by the ODI
 - Anxiety and Depression as assessed by the HADS
 - Pain Catastrophizing as assessed by the PCS
 - Medication Usage

Timing of visit	Activities at visit	Case Report Form
Screening/Baseline	 Subject assesses pre-trial pain levels, quality of life, disability, anxiety, depression, pain catastrophizing, and medication usage. 	 VAS Form EQ-5D Form ODI Form HADS Form PCS Form Medication Usage Form

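### The VAS reading that qualifies a subject at 6.0 cm is also the primary-endpoint baseline, so the reported change includes a modest regression to the mean that one extra VAS form could reduce or remove

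*Combined protocol and SAP*

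**What the plan says.** **Entry.** Section 5.4.1 (and the synopsis, 1.6.1) requires "at least 6.0 cm out of 10.0 cm on the average back and/or leg pain VAS at baseline". Under 6.3 a subject is enrolled only once every inclusion criterion is confirmed.

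**Primary endpoint.** Section 5.3.1: "Evaluate the change in pain intensity between baseline, trial and long-term follow up evaluations using the Visual Analog Scale (VAS) assessments". Section 7.1.1.1 analyses it by repeated measures ANOVA with Tukey comparisons, and 7.3 sets the error rate at 0.05.

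**Readings before stimulation.** The visit table in 6.4.1 has a single row, "Screening/Baseline", with one VAS form, and the text adds: "Baseline visit activities can occur at the same visit of enrollment after the informed consent has been obtained". In the flow chart (6.7) the row "VAS Assessment" is marked at Baseline, End of Trial and Follow-up only. Section 6.4.2 lists a surgery form and a programming form for the SCS Trial visit, but no VAS.

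**50% rule.** Section 6.4.2 defines adequate relief during the trial as "at least 50% reduction in back and/or leg VAS from baseline". Section 6.4.3 words its end-of-trial rule differently and names another reference: "If the VAS score is < 50% of the VAS collected during the screening visit".

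**Design and purpose.** The study is open label, and every subject starts on the same microdosing pattern (5.1). The primary objective is efficacy (5.2.1). Section 7.1 says no formal hypothesis testing is required and that the results may potentially feed a level-1 study. Section 7.6 says there are no formal success criteria.

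**The concern.** A single VAS score mixes a subject's usual pain level with day-to-day variation. If subjects enter only when one reading is at least 6.0 cm, the admitted group includes some whose reading was high by chance. Their next reading is lower on average even if nothing is done. When that same reading is the baseline, the fall is counted as improvement.

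A concurrent control would show the same fall, and it would cancel in the comparison. This trial has no control, run-in or repeat qualifying reading, and no correction in the analysis. The bias therefore enters the primary estimate, and it always favours the therapy. The mean change reported under the efficacy objective, and the 0.05-level contrasts between baseline and later visits, would both carry it.

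**Working it through.** **1. The plan's own figure.** There is none to reproduce. The documents give no effect size, SD, correlation, power or sample-size calculation (7.1.1.2).

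**2. Inputs.** From the documents: threshold 6.0 cm, scale 0 to 10 cm, up to 60 subjects, error rate 0.05 (taken here as two-sided; the plan does not say). Assumed: mean VAS among candidates μ = 5.5 to 7.0 cm, SD σ = 1.5 to 2.0 cm, retest correlation r = 0.6 to 0.8.

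**3. Formula, with zero treatment effect.** Let z = (6.0 − μ)/σ and λ = φ(z)/(1 − Φ(z)).
- Selected baseline mean = μ + σλ
- Expected fall at the next reading = (1 − r)σλ

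**4. Central case (μ = 6.5, σ = 2.0, r = 0.7).** z = −0.25 and λ = 0.3867/0.5987 = 0.646.
- Selected baseline mean = 6.5 + 2.0 × 0.646 = 7.79 cm
- Spurious fall = 0.3 × 1.29 = 0.39 cm, and 0.39/7.79 = 5.0%

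A simulation with scores held within 0 to 10 also gave 0.39 cm, so the ends of the scale matter little here.

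**5. Range.**

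| μ | σ | r | Selected mean (cm) | Spurious fall (cm) |
|---|---|---|---|---|
| 7.0 | 1.5 | 0.8 | 7.64 | 0.13 |
| 7.0 | 2.0 | 0.7 | 8.02 | 0.31 |
| 6.5 | 2.0 | 0.7 | 7.79 | 0.39 |
| 5.5 | 2.0 | 0.6 | 7.43 | 0.77 |

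A wider grid (μ 6.0 to 7.5, r 0.5 to 0.9) gives 0.04 to 0.80 cm.

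**6. Effect on a 0.05-level contrast.** The variance of the paired difference is (1 − r)²σ²(1 + zλ − λ²) + (1 − r²)σ². In the central case this is 0.15 + 2.04 = 2.19, so the SD is 1.48 cm. With 60 pairs the standard error is 1.48/√60 = 0.191, and the chance of a significant fall with no treatment effect is Φ(0.3875/0.191 − 1.96) = 53%. With 40 pairs it is 38%. The nominal figure in that direction is 2.5%. Over the grid in step 2 with 60 pairs the range is 19% to 97%. These are unadjusted paired contrasts. Tukey adjustment would lower the figures but does not remove a biased baseline.

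**7. Effect on the 50% rule.** With no treatment effect and two attempts, the simulated chance of passing against the selecting reading is 5.6% at μ = 6.5, σ = 2.0, r = 0.5, and 1.5% at r = 0.7. Against a separate reading it is 3.2% and 0.7%. If mean true relief is 50% with a between-subject SD of 25 points (both assumed), the central case gives 54% passing against the selecting reading and 50% against a fresh one. The effect is small.

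**8. What a second reading achieves.** Let r₁ be the correlation of the screening reading with the second reading and r₂ its correlation with later readings. The artefact left after the second reading is (r₁ − r₂)σλ. If the error in the second reading is independent of the first, r₁ = r₂ and nothing is left. If, say, r₁ = 0.8 and r₂ = 0.7 because the two readings are close in time, 0.1 × 1.29 = 0.13 cm of the 0.39 cm remains.

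**The case against.** The strongest reply is that this is a feasibility study with no success criteria, so no pass/fail decision turns on the bias, and that its size rests wholly on assumptions. Both statements are correct. The 0.77 cm end needs a candidate mean of 5.5 cm and SD of 2.0 cm, which implies that about 60% of candidates fail the threshold (1 − 0.401). Nothing in the documents supports that. What remains is that efficacy is the primary objective and tests at 0.05 are planned.

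The model is also simpler than the criterion. If the average VAS means recalled average pain, r rises and the bias shrinks; the plan does not define it. Either back or leg pain may qualify, and the primary endpoint names no site. A non-qualifying site is not directly truncated, while taking the worse site could enlarge the bias.

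It can be said that more than one early VAS may exist. The flow chart is incomplete (it has no medication or programming rows), 6.4.3 speaks of a screening visit, and the case report forms are kept separately. This is fair as a caution, but the combined row in 6.4.1 makes a single reading the natural interpretation.

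A reader might infer three stronger things that the documents do not support:
- **That regression to the mean could explain the whole benefit.** A subject entering at 6.0 cm needs a 3.0 cm fall to reach 50%. The artefact is under 1 cm throughout the assumed ranges.
- **That it materially loosens the 50% rule.** Step 7 of the working shows a minor effect.
- **That a later level-1 trial would inherit the inflated effect.** Section 7.1 speaks only of potential use, and in a controlled trial regression to the mean would affect both arms.

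**Conclusion.** The point holds in a limited form. As scheduled, one pre-stimulation VAS both selects subjects and starts the primary change, so the change from baseline in this uncontrolled trial includes some regression to the mean. Its direction is known: it favours the therapy. Its size is not known from the documents. Under the stated assumptions it is about 0.13 to 0.77 cm, with 0.39 cm (5% of a 7.79 cm selected mean) in a central case. It can make a baseline contrast significant by itself, but it is small against the relief the trial looks for. It is worth correcting because the correction is cheap.

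**What to change.** - Keep the 6.0 cm rule on the screening VAS, for eligibility only.
- Add one VAS form at the SCS Trial visit before lead placement, preferably on a different day from screening (6.4.2 and one mark in the 6.7 flow chart).
- In 5.3.1, define that second reading as baseline for the primary endpoint, and report the change from the screening reading as a sensitivity result. Subjects below 6.0 cm on the second reading stay eligible.
- Reconcile Section 6, 6.4.2 and 6.4.3 on which reading the 50% rule refers to. That choice is the sponsor's. If it differs from the primary baseline, the report should say so.
- State in the report that the whole change is not attributed to microdosing. Placebo response, natural course and follow-up restricted to subjects who pass the trial are untouched by this fix.

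**Cost.** One more form at a visit that already takes place, with no new visit. The reported reduction may be slightly smaller. The new baseline would be taken in a pre-procedure setting, unlike the clinic follow-ups. The plan sets no interval between the Baseline and SCS Trial visits, and if they are close together part of the artefact stays.
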